## 2.0 HYPOTHESIS AND AIMS

The hypothesis is that diluted 4:1 cardioplegia used in adult cardiac surgery at Washington University in St. Louis contributes to increased transfusion rates peri-operatively and incorporation of Quest, Inc. microplegia may decrease RBC transfusion rates, and thus, impact overall morbidity and mortality after cardiac surgery.

Specific aims are:

1. To determine if use of microplegia results in less peri-operative transfusions compared to diluted 4:1 cardioplegia.
2. To investigate the effects of microplegia on overall morbidity and mortality during the peri-operative period. We will assess operative mortality and 30 day mortality. We will examine intra-operative and post-operative complications. A complete list of variables to be examined can be found in table 1. We will determine if microplegia results in better myocardial protection than standard cardioplegia by assessing pre-operative, intra-operative and post-operative serum troponin levels.

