### **5.0 STUDY DESIGN**

The hypothesis will be accomplished in a randomized, blinded, prospective institutional study conducted at two sites, Barnes Jewish Hospital and Christian Northeast Hospital. 314 patients will be randomized to either receive diluted 4:1 cardioplegia or nondiluted microplegia. This will be a blinded study to both the patient and surgeon. The patient will be randomized during the preoperative period. Quest Medical Inc. will supply us with the microplegia MPS-2 machines needed to conduct this study. Outcomes will be measured by a blinded clinician.

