***Peri-operative period***

Troponins will be drawn in the operating room prior to initiation of cardiac surgery and post-operatively upon arrival to the ICU, 12 hours, and 24 hours.

Subjects will undergo their standard of care, planned cardiac surgery procedure as directed by their treating surgeon.

Given that our primary endpoint is transfusion requirement, we will assess this need throughout the entire peri-operative period. Standard blood draws after surgery to evaluate hematocrit will be used for analysis. We will use the electronic medical records to obtain this information.

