**6.0 OUTCOME MEASURES (DATA)**

Data will be obtained from the electronic medical record system at Washington University. Study staff from each participating site will review the subject's medical record and obtain the study-specific data to include but is not limited to the following. For a complete list of all data variables to be collected please see table 1. The study-specific data will be collected by the study staff and entered into a REDCap database that will be created specifically for this study. REDCap is a mature, secure web application for building and maintaining databases (<https://redcap.wustl.edu>).

Electronic study data will be entered in a secure REDCap database. Only investigators and the study team for this study will have access to the study data. They will each use a unique log-in ID and password that will be kept confidential.

See Appendix 3: Data Collection for Table 1

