## **9.0      STATISTICAL ANALYSIS**

Continuous variables will be expressed as mean  $\pm$  standard deviation or as median with range. Categorical variables will be expressed as frequencies and percentages with outcomes compared using the  $\chi^2$  or the Fisher exact test. Continuous outcomes will be compared using the *t* test for means of normally distributed continuous variables and the Mann-Whitney U nonparametric test for skewed distributions. Significant covariates on univariate analysis ( $p \leq 0.10$ ) or covariates deemed clinically relevant based on experience will be entered into a multivariate binary logistic regression analysis.

A sample size of 314 patients will be randomized to either receive standard 4:1 cardioplegia or microplegia. The sample size was calculated based on a one tailed test with alpha 0.05 and beta 0.2 (80% power) to detect a 25% relative risk reduction in pRBC units transfused. An interim analysis will be completed following the enrollment of 150 patients.

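### The covariate rule for the logistic model is not limited to variables the assigned arm cannot affect, and the model's outcome and rank are not stated

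*Combined protocol and SAP*

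**What the plan says.** Section 9.0 compares outcomes with unadjusted tests: chi-square or Fisher for categorical outcomes, and t or Mann-Whitney for continuous ones. It then gives two routes into a logistic model. "Significant covariates on univariate analysis" enter at p ≤ 0.10, and "covariates deemed clinically relevant based on experience will be entered into a multivariate binary logistic regression analysis". There is no covariate list and no limit on when a covariate is measured. The section does not name the model's outcome, does not say that arm is a term in it, and does not say how it ranks beside the unadjusted tests.

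The sample size was set "to detect a 25% relative risk reduction", applied to units of packed red cells, with no control rate, mean or SD. The section also states: "An interim analysis will be completed following the enrollment of 150 patients".

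On timing, section 5.0 states: "The patient will be randomized during the preoperative period". Section 2.0 hypothesises that diluted cardioplegia "contributes to increased transfusion rates peri-operatively".

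The only variable list is Table 1 in Appendix 3. Section 6.0 presents it as a data-collection list: "For a complete list of all data variables to be collected please see table 1". Its intra-operative column includes on-CPB hematocrit, crystalloid total and the amount of cardioplegia or microplegia delivered. Appendix 1 makes an on-bypass hematocrit below 20%, predicted or actual, an intra-operative transfusion trigger.

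On troponin, section 5.0 (Peri-operative period) states: "Troponins will be drawn in the operating room prior to initiation of cardiac surgery". Further samples follow on ICU arrival and at 12 and 24 hours.

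**The concern.** The arms differ in dilution, and the hypothesis is that dilution leads to transfusion. Hematocrit during bypass is a plausible step between the two, and the protocol makes it a trigger. It is therefore a strong candidate under both entry routes: it should predict transfusion, and clinicians would call it relevant. Crystalloid total and cardioplegia volume may simply describe which treatment was given. A univariate p-value cannot tell a prognostic baseline factor from a consequence of treatment.

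If such a variable enters a model meant to estimate the treatment effect, part of that effect is adjusted away, or the estimate is biased in some other way. The adjusted and unadjusted results could then disagree on transfusion, and no rule in the plan says which one counts. The experience clause also leaves the covariate set open after outcome data have been seen.

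**Working it through.** **1. Text check.** Randomisation is pre-operative, so anything measured in theatre comes after it. What matters is whether the arm can affect the variable:

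- On-CPB hematocrit: it can, if read after cardioplegia starts. The documents do not say when it is read.
- Crystalloid total and cardioplegia volume: they may describe the treatment itself.
- Type of surgery and concomitant procedures: Table 1 files these as intra-operative, but the planned procedure can be known before randomisation.
- Operating-room troponin before surgery starts: it may follow randomisation but precedes cardioplegia, so the arm cannot affect it.

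No section restricts the covariates.

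**2. The plan's own figure.** The 314 cannot be derived directly, because no control rate or SD is given. Back-solving for a binary endpoint (one-sided 0.05, 80% power, 1:1 allocation, pooled formula, no continuity correction), 56% against 0.75 × 56% = 42% gives

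n = [1.645·√(2 × 0.49 × 0.51) + 0.842·√(0.56 × 0.44 + 0.42 × 0.58)]² / 0.14² = 156.6,

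so 157 per arm and 314 in total. This is not the only solution. For mean units with a coefficient of variation of 0.89, n = 2 × (1.645 + 0.842)² × (0.89/0.25)² = 156.7, which also gives 314. The binary version is used below because the stated model is logistic.

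**3. Illustration (all hematocrit inputs assumed).** Baseline hematocrit is N(38, 5). On-CPB hematocrit is M = 0.65 × baseline + shift × arm + N(0, 2). The logit of transfusion risk is a − 0.35 × (M − mean) + direct × arm. The intercept a and total effect T = −0.757 are solved to give 56% and 42%. For a share s carried by M, shift = −T·s/0.35 and direct = T·(1 − s). There are 4,000 simulated trials of 157 per arm for each setting, tested one-sided at 0.05.

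| Share carried | Arm difference in M (points) | Unadjusted power | Baseline-adjusted | Plus on-CPB hematocrit |
|---|---|---|---|---|
| 0% | 0 | 80% | 86% | 89% |
| 10% | 0.22 | 80% | 86% | 82% |
| 25% | 0.54 | 79% | 86% | 68% |
| 50% | 1.08 | 80% | 87% | 41% |

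The baseline-adjusted log odds ratio is about −0.70. With M added it becomes −0.57 at 25% and −0.39 at 50%. M passed the p ≤ 0.10 screen in every run at shares of 25% and above. Among trials with a significant unadjusted test, the model with M was not significant in 18% (25% share) and 49% (50% share), against 2–3% with baseline hematocrit alone.

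**4. Sensitivity.**

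- With a weaker slope (0.10 per point), power with M is 73% against 81% baseline-adjusted at a 10% share. At 25% and 50% it is 55% and 26%, against 79–82%. This slope needs larger arm differences in hematocrit for the same share.
- If some patients are transfused on bypass before the reading (50% share), the adjusted log odds ratio runs from −0.59 to −0.89 against −0.70. The bias can go either way.

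**5. Troponin.** Adjusting for a baseline value with correlation ρ cuts residual variance by ρ²: 1%, 9%, 25% and 49% for ρ = 0.1, 0.3, 0.5 and 0.7. These correlations are assumed.

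**The case against.** The strongest reply is that harm requires a chain of conditions. The model must estimate the treatment effect, an intra-operative variable must be chosen, it must be read after cardioplegia starts, and it must carry a material share of the effect. The plan states none of these. A single sentence about significant covariates also fits a risk-factor model, where intra-operative predictors are legitimate. All of this stands, and it makes the point conditional. It does not remove the gap, because the plan does not say which kind of model is meant.

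The endpoint objection also stands. The plan sizes the trial on units transfused, so 56% against 42% is an assumption. If the primary endpoint is a count, these power figures do not describe the primary comparison.

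Four stronger readings are tempting, and the documents do not support them:

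- *That the main result is compromised.* The unadjusted tests do not depend on the covariate rule.
- *That on-CPB hematocrit will be entered.* Table 1 is a data-collection list, not a declared covariate pool.
- *That the adjusted effect would nearly vanish.* With 75% or 100% of the effect carried, the same model gives power of 17% and 5%. But the assumed on-CPB mean is 0.65 × 38 = 24.7 and the SD is √(3.25² + 2²) = 3.8, so only about 11% of controls fall below the 20% trigger, against 56% transfused. The post-operative triggers in Appendix 1 use hemoglobin, symptoms, renal failure and bleeding. Shares that high are extreme cases.
- *That the logistic model will be run, or its covariates chosen, at the interim.* Section 9.0 does not say so; it only leaves the choice undated.

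**Conclusion.** The gap holds on the text alone: the selection rule has no limit to variables the arm cannot affect, and the model's outcome and rank are unstated. The consequence is conditional and confined to the adjusted estimate. Under the assumed inputs, the loss against baseline adjustment is about 4 percentage points of power if on-CPB hematocrit carries 10% of the effect, 18 points at 25% and 46 points at 50%. A reading taken before cardioplegia costs nothing. The direction of bias is not fixed if transfusion can precede the reading. The documents give no hematocrit distribution, slope, carried share or reading time, so these figures show what could happen and do not forecast it. The plan should be changed, but this is not a fatal flaw.

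**What to change.** Replace the selection sentence in section 9.0 with:

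> The unadjusted comparison of the primary transfusion endpoint is the primary test. A supportive regression model suited to that endpoint (logistic if it is any pRBC transfusion) includes arm and a short list of covariates the arm cannot affect, fixed before the interim analysis at 150 patients (for example pre-operative hematocrit, sex, weight, creatinine, site and planned type of surgery). Variables measured after cardioplegia starts do not enter any treatment-effect model; risk-factor or mediator models are exploratory.

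The criterion is whether the arm can affect the variable, not Table 1's column label. A ban on the whole intra-operative column would wrongly exclude the planned type of surgery, which may matter because section 3.0 admits any non-emergent cardiac surgery.

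Separately, adjust the post-operative troponin comparison for the troponin drawn before surgery starts, on the log scale if skewed.

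The cost is wording only. Pre-operative hematocrit, sex, weight, creatinine and troponin are in Table 1's pre-operative column, site is known, type of surgery is already recorded, and the sample size stays at 314. In the illustration, baseline adjustment raises power from about 80% to 86–87%. The downside is that the covariate list can no longer be adapted to the data.

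### Does the primary transfusion test lack a significance rule because one-tailed alpha 0.05 appears only in the sample-size sentence?

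*Combined protocol and SAP*

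**What the plan says.** Section 9.0 is the whole statistical plan. Its first paragraph names the tests. For categorical data it says "Categorical variables will be expressed as frequencies and percentages with outcomes compared using the" chi-square or Fisher exact test. For continuous outcomes it names the *t* "test for means of normally distributed continuous variables and the Mann-Whitney U nonparametric test for skewed distributions". Neither sentence gives a direction or a significance level. The only threshold in that paragraph is p ≤ 0.10, which governs "Significant covariates on univariate analysis" and their entry into a logistic regression.

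The second paragraph gives the design basis: "The sample size was calculated based on a one tailed test with alpha 0.05", with 80% power, "to detect a 25% relative risk reduction in pRBC units transfused", and a total of 314. It adds: "An interim analysis will be completed following the enrollment of 150 patients".

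Section 2.0 sets two aims. Aim 1 has a direction: "To determine if use of microplegia results in less peri-operative transfusions compared to diluted 4:1 cardioplegia". Aim 2 has none: "To investigate the effects of microplegia on overall morbidity and mortality during the peri-operative period". Section 5.0, under the peri-operative period, makes transfusion requirement the primary endpoint.

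**The concern.** Read literally, the one-tailed 0.05 describes how the trial was sized, and the tests that will be run carry no decision rule. Chi-square makes this look worse, because on a 2×2 table it has no direction. Run at 0.05 in the ordinary way, it rejects above 3.841 for a difference either way. The one-tailed rule needs a cut-off of 2.706 and a check that microplegia had fewer transfusions. The same list of tests also serves Aim 2, which has no direction, so the one-tailed sentence cannot be meant for every comparison.

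What would be at stake is the primary verdict. A result favouring microplegia with a direction-free p between 0.05 and 0.10 is positive under the sizing rule and negative if the ordinary chi-square p is read at 0.05. If the rule were picked after the data were seen, the conclusion could go either way.

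**Working it through.** **Inputs from the documents.** Total 314, one-tailed alpha 0.05, power 80% and a 25% relative reduction (Section 9.0). **Assumptions.** 1:1 allocation (157 per arm), since no ratio is stated. A control rate, or a mean and SD, must also be assumed, since none is given.

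**1. Can 314 be reproduced, and does it reveal the direction?** For a yes/no endpoint the size per arm is

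n = [z(α)·√(2p̄(1−p̄)) + z(power)·√(p₁(1−p₁) + p₂(1−p₂))]² / (p₁−p₂)².

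- One-tailed, 56% vs 42% (p̄ = 0.49): [1.645 × √0.4998 + 0.842 × √0.4900]² / 0.14² = 156.6, so 157 per arm and 314 in total.
- Two-sided, 62.8% vs 47.1%: the same formula with 1.960 also gives 314.
- For mean units, n = 2[(z(α) + z(power)) × (SD/mean) / 0.25]². One-tailed with SD/mean 0.89: 2 × (2.486 × 0.89 / 0.25)² = 156.7, again 314. Two-sided needs SD/mean of about 0.79.

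The number 314 fits either kind of test, depending on the unstated control rate or SD. The direction has to come from the wording.

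**2. The disputed zone.** One-tailed 0.05 means z > 1.645, and 1.645² = 2.706. Two-sided 0.05 means |z| > 1.960, and 1.960² = 3.841. The two readings differ only when microplegia has fewer transfusions and z lies between 1.645 and 1.960. With more transfusions on microplegia, neither reading gives a claim of benefit.

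**3. The zone in patients.** Illustration with 157 per arm and 88 control patients transfused (88/157 = 56.1%), chi-square without continuity correction:

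| Fewer transfused on microplegia | Chi-square | Direction-free p | One-tailed p |
|---|---|---|---|
| 14 | 2.50 | 0.114 | 0.057 |
| 15 | 2.87 | 0.090 | 0.045 |
| 16 | 3.26 | 0.071 | 0.035 |
| 17 | 3.68 | 0.055 | 0.027 |
| 18 | 4.13 | 0.042 | 0.021 |

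Only 15, 16 and 17 fewer (17% to 19% relative reduction) separate the readings. The band depends on the test. With Fisher's exact test on the same tables, 15 fewer has one-sided p 0.057 and 18 fewer has two-sided p 0.055, so the band moves to 16 to 18 fewer.

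**4. How often it would matter.** If the stated 80% is right, the expected z is 1.645 + 0.842 = 2.486 (unrounded terms). The chance of exceeding 1.960 is Φ(2.486 − 1.960) = 70.1%, so 80.0% − 70.1% = 9.9% of such trials fall in the zone. With no true effect the figure is 5.0% − 2.5% = 2.5%.

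**5. Does the plan leave the choice open?** Setting the statements side by side:

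- The sizing sentence attaches one-tailed 0.05 to pRBC units transfused, which is the transfusion comparison.
- Section 5.0 makes transfusion requirement primary.
- Aim 1 asks whether microplegia gives fewer transfusions, the same direction.
- No section mentions two-sided testing.
- The 0.10 threshold is for choosing covariates and would not be taken for the primary alpha.

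Three of the four named tests (*t*, Mann-Whitney U, Fisher exact) have a one-tailed form. For chi-square, the signed square root compared with 1.645 gives the same rule. If the primary variable is units, as the sizing sentence suggests, chi-square does not arise at all.

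**The case for a change.** The strongest case for acting is that the rule is inferred. The sizing sentence looks back at a calculation, while the test sentences look forward and are silent. An analyst who ran the named chi-square at 0.05 would be testing two-sided without departing from any written rule. The sample size cannot arbitrate, as step 1 shows. A 9.9% chance of landing in the zone is not remote, and one sentence written before outcomes are compared would close it at no cost in patients.

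Much of this stands. The test sentences are silent, the arithmetic is right, and a confirming sentence would do no harm. It is also true that the plan does not say whether the primary variable is any transfusion or the number of units, and so which test applies.

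It does not stand as a reason to change the plan. A statement that a trial is sized on a one-tailed 0.05 test is ordinarily read as describing its primary test, and every related statement here agrees with it. The two-sided alternative is nowhere in the text. Aim 2's lack of direction leaves the Aim 1 rule untouched. The interim look has no stated purpose and is a separate matter, since it does not alter the direction of the final test. The proposed sentence would only restate the rule the plan already implies.

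**Conclusion.** The concern describes a real silence but calls for no change. Section 9.0 does not repeat the direction and level beside the tests, yet its sizing sentence and Aim 1 supply them: the primary transfusion comparison is one-tailed at 0.05 in favour of microplegia. Following that rule keeps 314 patients, leaves the stated 80% power as it is, and holds the false-claim rate at 5% for a single final test.

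The silence could affect only favourable results with z from 1.645 to 1.960. That is about 9.9% of trials under the design effect if the stated power is right, and in the illustration 15 to 17 fewer patients transfused. The patient counts rest on an assumed 1:1 allocation, an assumed control rate and an uncorrected chi-square. The 9.9% rests on the stated 80%, which cannot be checked without a control rate or a mean and SD. The concern offers no better method and shows no error, so this is detail that an analyst fills from the plan's own text.

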**Postoperative:**

1. It is appropriate to transfuse if hemoglobin falls below 7 g/dL
2. It is appropriate to transfuse if hemoglobin falls below 8 g/dL and any of the following are present:
  - patient has borderline hemodynamics, or has become dependent upon pressors/inotropes
  - patient is symptomatic (i.e. dizziness, lightheadedness, unable to ambulate)
  - patient is in acute renal failure
3. It is appropriate to transfuse in any case of ongoing hemorrhage/acute blood loss

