## 15.0 Appendix 3: Data Collection

**Table 1:** Baseline pre-operative, operative, and post-operative variables to be examined.

Pre-operative variables	Intra-Operative Variables	Post-Operative Variables
Age	pRBC transfusion (see appendix 2, peri-operative transfusion form): date, number of units, name of staff ordering transfusion, actual/predicted hematocrit, justification if hematocrit >20%	pRBC transfusion (see appendix 2, perioperative transfusion form): date, number of units, name of staff ordering transfusion, hemoglobin level, justification if hemoglobin $\geq 7.0$ g/dL.
Weight	Platelet transfusion: number of units	Platelet transfusion: number of units
Dyslipidemia	FFP transfusion: number of units	FFP transfusion: number of units
Hypertension	Mortality	Hematocrit on arrival to ICU
COPD	Clamp time	Hematocrit 24 hours post-operatively
Coronary artery disease	Amount of cardioplegia/microplegia delivered	30 day mortality
Liver disease	Type of surgery	Time on ventilator
Cerebrovascular disease	CPB time	Hours in the intensive care unit
Previous cardiac interventions	Cross-clamp time	Length of hospital stay
History of arrhythmia	Cardioplegia technique	Renal failure
Diabetes mellitus	Number of grafts	Pulmonary complications
LVEF (%)	Concomitant procedures	Low output syndrome
Congestive heart failure	Pre-CPB hematocrit	Myocardial infarction
Peripheral vascular disease	On-CPB hematocrit	Serial troponins: arrival to ICU, 12 and 24 hours post-op
Hemoglobin, hematocrit	Post-CPB hematocrit	New onset post-op atrial fibrillation
Creatinine	Date of surgery	Stroke
Troponin	Skin incision to skin close time	Mortality
Previous PCI +/- stents	Cardioplegia Delivery	Readmission
Angina	Additive Volume	Readmission date
BMI	Arrest Agent Volume	Readmission reason
Height	Total CDPG	
Ethnicity	Crystalloid Amount	
Race	Crystalloid Total	
Chronic Lung Disease	Anesthesiologist	
Immunocompromise	Perfusionist	
Mediastinal Radiation	Starting glucose	

Thoracic Aorta Disease	Final glucose	
Sex	TEE score	
Date of admission	Time to arrest	
	Volume to arrest	
	Cryoprecipitate volume	Cryoprecipitate volume

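### The 80% power behind 314 patients cannot be verified: the effect mixes a proportion measure with a unit count, and no control rate, mean or SD is given

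*Combined protocol and SAP*

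**What the plan says.** Section 9.0 holds the only sample-size justification. It states that "A sample size of 314 patients will be randomized to either receive standard 4:1 cardioplegia or microplegia" and rests this on a "one tailed test with alpha 0.05 and beta 0.2 (80% power) to detect a 25% relative risk reduction in pRBC units transfused". It gives no allocation ratio, dropout allowance, control-arm transfusion rate, mean number of units, SD or source. Section 1.0 says only, in qualitative terms, that transfusion is common in cardiac surgery.

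The scale of the primary endpoint is not settled elsewhere. Section 5.0 (Peri-operative period) says: "Given that our primary endpoint is transfusion requirement, we will assess this need throughout the entire peri-operative period". Section 2.0 speaks of transfusion rates and of fewer transfusions. The forms in Appendix 2 record the number of pRBC units at each transfusion, so either a yes/no endpoint or a unit count could be derived.

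For analysis, Section 9.0 lists chi-square or Fisher tests for categorical outcomes and t or Mann-Whitney tests for continuous ones. A binary logistic regression follows, with covariates that reach p ≤ 0.10 on univariate analysis or are judged clinically relevant. It does not say which of these is the primary comparison.

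**The concern.** The phrase "25% relative risk reduction in pRBC units transfused" joins two scales that need different inputs. A yes/no endpoint needs the control proportion. A unit count needs a mean and a measure of spread, and patients who receive no blood enter as zeros, which widens that spread. At the same N, the two readings can give quite different power.

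At stake is how a non-significant result would be read. If the trial is taken to have had 80% power for a 25% reduction, a null result will count as evidence against microplegia. That inference is sound only if the unstated control figures were near the values that make 314 work on the scale actually analysed.

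**Working it through.** **Inputs from Section 9.0:** N = 314; "one tailed test with alpha 0.05"; power 80%; 25% relative reduction. **Assumed, because not stated:** 1:1 allocation (157 per arm), no dropout, no adjustment for the interim analysis. Normal quantiles: 1.645 and 0.842; (1.645 + 0.842)² = 6.183.

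The stated figure cannot be reproduced from the plan's own inputs, so the missing input is solved for on each scale.

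**1. Proportion transfused.** With p₂ = 0.75 p₁ and p̄ their mean,

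n per arm = [1.645 √(2p̄(1−p̄)) + 0.842 √(p₁(1−p₁) + p₂(1−p₂))]² / (p₁ − p₂)².

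At p₁ = 0.56, p₂ = 0.42, p̄ = 0.49: (1.645 × 0.707 + 0.842 × 0.700)² / 0.14² = 3.07 / 0.0196 = 156.6, so 157 per arm and 314 in total. The matching control rate is about 55.5% with the unpooled formula and about 58.5% with a continuity correction.

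| Control rate | Power at 157 per arm | N for 80% |
|---|---|---|
| 40% | 58% | 562 |
| 50% | 72% | 388 |
| 56% | 80% | 314 |
| 60% | 85% | 272 |

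**2. Mean units.** Work in multiples of the control mean, so the difference is 0.25 and the control SD is the CV.

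- Equal SDs: CV² = 157 × 0.0625 / (2 × 6.183) = 0.794, so CV = 0.89.
- Equal CVs (SD falls with the mean): the variances sum to CV² × (1 + 0.75²) = 1.5625 CV². Then CV² = 157 × 0.0625 / (1.5625 × 6.183) = 1.016, so CV = 1.01.

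| CV of units | Power, equal SDs | Power, equal CVs |
|---|---|---|
| 0.8 | 87% | 93% |
| 1.0 | 72% | 81% |
| 1.25 | 55% | 64% |
| 1.5 | 43% | 51% |

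A Poisson count with a control mean of about 1.1 units also gives 157 per arm. So 314 fits more than one reading.

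**3. How the two scales relate.** If a share π is transfused and units among those patients have CV c, then CV² = (1 + c²)/π − 1 over all patients. Power below runs from equal SDs to equal CVs.

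| π | c | Overall CV | Power on units |
|---|---|---|---|
| 56% | 0.3 | 0.97 | 74–82% |
| 56% | 0.5 | 1.11 | 64–73% |
| 56% | 0.7 | 1.29 | 53–62% |
| 75% | 0.5 | 0.82 | 86–92% |
| 80% | 0.7 | 0.93 | 77–85% |

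Power on units can fall on either side of 80%. The documents give neither π nor c.

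**4. What a baseline covariate could recover.** Table 1 in Appendix 3 lists "Hemoglobin, hematocrit" among the pre-operative variables. The Appendix 1 triggers act on hematocrit (intraoperatively) and hemoglobin (postoperatively, for example "It is appropriate to transfuse if hemoglobin falls below 7 g/dL"), so the pre-operative value is their starting point. In a simulation with 157 per arm and unadjusted power of about 80% for any transfusion, adjusting for a covariate that explains 20–40% of latent transfusion risk raised power to about 86–89%. For units the gain was about 2–5 points. The 20–40% is an assumption.

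**The case against.** The strongest defence is that the endpoint was meant as yes/no. Relative risk, transfusion rates, transfusion requirement and a planned binary logistic regression all point that way. On that reading 314 is coherent at a control rate near 56%, and the mention of units is loose wording. Much of this stands, and it is why the point concerns verifiability. It does not close the gap, because the control rate is still missing and a fall from 56% to 50% takes power from 80% to 72%.

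A reader might go further and infer that 314 works only as a proportion, or that power on units is in fact below 80%. Neither is supported. 314 also fits mean units at a CV of 0.89 to 1.01. Using the 56% to fault the units reading carries a figure solved under one reading into the other. If the sponsor sized on units, nothing ties the control rate to 56%; at 75% transfused with c = 0.5, power on units is 86–92%. Even at 56%, the equal-CV case gives 82% at c = 0.3. The layout of the transfusion forms says nothing about how widely unit numbers vary, and the postoperative form provides for further entries.

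It is also fair to say that Section 9.0 already admits clinically relevant covariates to its regression. But it neither names hematocrit nor makes the adjusted model the primary comparison.

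**Conclusion.** The point holds as a gap in the justification. No number printed in the plan is shown to be wrong. The stated 80% is conditional on an unnamed scale and an unstated control figure, so it cannot be checked. Depending on assumptions the documents leave open, the power of 314 for a 25% reduction runs from 58% to 85% for control rates of 40% to 60%, and from 43% to 93% for unit CVs of 1.5 down to 0.8. Power on units is unknown; it has not been shown to fall short.

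All figures assume 1:1 allocation, no dropout and normal approximations, and they ignore the interim analysis. The sponsor should correct this before the data are analysed.

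**What to change.** Keep N at 314 and revise Section 9.0.

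1. Make the primary comparison a single pre-specified model adjusted for pre-operative hematocrit: logistic regression if the endpoint is any pRBC transfusion, a count model if it is units. This replaces an unadjusted test followed by covariate screening at p ≤ 0.10. The expected gain is about 6–9 power points for any transfusion, if hematocrit explains 20–40% of latent risk, and less for units.
2. Name the primary variable (any transfusion or number of units), supply the control figure and its source, and restate the power of 314 on that scale as conditional on that figure. The 56% solved for here should not be written in as though it had been the sponsor's assumption.
3. Optionally, at the planned 150-patient point, compute the pooled, blinded proportion transfused and the CV of units, and report the updated detectable effect. Because the arms are not compared, this costs no alpha.

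The cost is protocol wording, one covariate that is already collected and, if chosen, one blinded calculation. No extra patients are needed. The drawback is that the stated power may become less favourable.
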